#### **4.3.d Data Analysis for Aims 1 and 2**

For the primary evaluation aims for determining the optimal strategy for testing Latinx communities and the four adaptive intervention strategies, we will employ standard normal theory generalized linear modeling analysis of covariance fractional factorial analyses using pre-post assessment scores for site and individual level outcomes. Research Question 1 will focus on the combined effects of A1 randomization groups [(A+B+C+D) vs (E+F+G+H)]. Research Question 2 will focus on which A2 strategy works best for slow-responding sites [(D+H) vs (C+G)]. To address the non-independence of subjects in the embedded adaptive intervention designs and crossed factors, we will estimate linear mixed models with weighted least squares using the design effects coding shown in Table 4.3.1.

The general equation to estimate the optimal strategy is given by

$$E[Y|A_1, A_2, O_1] = \beta_0 + \beta_1 A_1 + \beta_2 A_2 + \beta_3 A_1 A_2 + \gamma^T O_1$$

where  $E$  is the expected value of the outcome,  $A_1$  is the initial treatment randomization,  $A_2$  is the second stage treatment randomization and  $\gamma^T$  are the estimates for covariate  $O_1$ , the pre-test covariate. For binary and count data we will employ generalized linear modeling and logit, probit, and poisson link functions for criterion outcomes such as frequency of tests, re-tests, and discrete event behaviors.

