Within the SMART, a measure of initial response is assessed following implementation of the primary outreach approaches in order to evaluate each site's need for further adaptation. In this way, testing is tailored to meet the needs of communities and their Latinx individuals and families by providing enhanced testing strategies to slow-responding sites. This measure of initial response is referred to as a primary tailoring variable. In the proposed study, the primary tailoring variable is whether a site is operating at a threshold of 80% testing capacity, based on the frequency and per capita testing rates and presumption of 50 tests per testing event. The AIS each represent distinct plans of testing outreach approaches. Within the SMART, it is then possible to evaluate which adaptive sequence is the most effective in impacting Latinx testing rates and secondary outcomes such as health maintenance behaviors.

Specifically, the proposed RADx SMART includes 4 embedded adaptive intervention strategies (AIS). Sites and individuals in the proposed Latinx sampling frame will receive one of two first-stage implementation outreach strategies: Basic Outreach approaches or Basic Outreach plus Promotoras Comunitarias. Primary outcomes will be site level testing rates and individual level COVID-19-related health behaviors. After the initial 4 weeks (2 testing events), sites will be re-randomized in the second-stage randomization to either stay the course stationary events or to a mobilization intervention. Thus, for the primary criterion outcome of testing capacity, the SMART design includes 4 embedded site level adaptive intervention strategies (AIS): (1) starting with culturally adapted Basic Outreach, and staying the course; (2) starting with Basic Outreach followed by mobilization intervention; (3) starting with Basic Outreach plus Promotoras Comunitarias and staying the course; and (4) starting with Basic Outreach plus Promotoras Comunitarias plus mobilization intervention. In addition, as a booster to the Promotoras Comunitarias intervention, for health behavior outcomes, individuals tested at Basic Outreach sites will receive pamphlet health promotion pamphlets, and those tested at Promotoras Comunitarias sites, will receive a health pamphlet plus a Promotoras de Salud intervention.

[figure not shown]

Figure 4.3.1

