#### 4.3.f Power

Power for detecting the optimal AIS was estimated using the SMARTAR package 1.0.0 in R R^71. We chose a power convention of .80 with a two-sided alpha level of .05 to reduce the probability of obtaining a false positive (Type-I error). For research question 1, balanced response rates of 50% of sites having adequate response and 50% slow responding, 36 sites for a continuous outcome (e.g., rates) can minimally detect a small difference of .27 among the combined group comparisons [(A+B+C+D) vs (E+F+G+H)], and power to minimally detect a medium effect of .54 (n=18 sites) [(D+H) vs (C+G)]. For the global test of the optimal treatment strategy (n=36 sites), the study is powered to minimally detect an effect of .40, a moderate effect. Power for detecting the optimal AIS was estimated using the SMARTAR package 1.0.0 in R^71.

We must also consider response scenarios that include either more slow-responding or even less slow responding sites before the tailoring intervention (i.e., 80% of the randomly allocated sites responded at capacity and 20% were below threshold; or alternatively, only 20% responded and 80% were below capacity initially). In each of these "unbalanced" response scenarios, power for research question 1 is the same as the balanced design above. Although we do not anticipate such a large range of slow responding sites based on our preliminary testing; for the slow-responding sites only, a bracket range of 80/20 response ratio (resulting in 8 slow responding sites [(D+H) vs (C+G)]) to a high of 20/80 ratio (resulting in 28 slow responding sites [(D+H) vs (C+G)]). In these scenarios, for research question 2, the study is powered .80 to minimally detect a difference of 1.3 (a large effect) or to minimally detect a moderate effect of .35 (a moderate effect), respectively, for 8 to 28 total slow responding sites for research question 2.

[figure not shown]

Figure 4.3.f Power Curve.

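### One undefined covariate, O1, cannot serve both randomizations: Question 2 on site testing should name each slow site's early testing score as its own covariate

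*SAP*

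**What the plan says.** SAP 4.3.d plans an analysis of covariance on pre-post scores, for site and individual outcomes, under a heading that covers Aims 1 and 2. It prints one general equation, with terms for A1, A2, their product and O1. O1 is described only as a pre-test covariate; neither the variable nor its time point is given. For the second question it says "Research Question 2 will focus on which A2 strategy works best for slow-responding sites [(D+H) vs (C+G", and it prints no separate model for that contrast.

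SAP 4.3.a fixes the order of events: "After the initial 4 weeks (2 testing events), sites will be re-randomized in the second-stage randomization". Initial response is assessed at that point. It enters the plan as a yes/no tailoring variable, whether the site runs at 80% of capacity, presuming 50 tests per event.

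SAP 4.3.f gives the number of sites in the contrast: 18 in the balanced case, and otherwise "respectively, for 8 to 28 total slow responding sites for research question 2". It states no correlation between early and later testing.

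**The concern.** A site's testing score over the first two events is measured after A1 and before A2. Its standing therefore differs between the two questions.

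- For Question 2 it is a baseline. Adjusting the mobilization contrast for it introduces no bias and removes variation among slow sites that the cutoff leaves in.
- For Question 1 it is a post-randomization variable. Adjusting for it would absorb part of the promotores effect.

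So whichever way O1 is read, the shared equation needs a change. If O1 is a score from before A1, as its subscript suggests, Question 2 omits the most relevant baseline. If O1 is the early score, Question 1 is adjusted for something the intervention may have moved. Question 2 has few sites, so its precision deserves care. The choice should be made before outcomes are seen, because adding or dropping a covariate afterward would be data-driven.

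**Working it through.** **Inputs.** From SAP 4.3.f: "power convention of .80 with a two-sided alpha level of .05"; 8, 18 or 28 slow sites, with 20%, 50% or 80% of sites slow. Assumed, because the documents do not say: 1:1 allocation of A2 among slow sites, approximate normality, and an early-late correlation r over all sites of .5 to .7. Differences are in SDs of the later testing outcome among slow sites.

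**The plan's own figures.** The SAP states "power to minimally detect a medium effect of .54 (n=18 sites"), 1.3 for 8 sites and .35 for 28. Read as standardized differences, these do not reproduce. The two-group formula (1.96 + 0.84) × √(4/n) gives 1.98, 1.32 and 1.06 for 8, 18 and 28 sites. The SAP does not name its effect scale, so I compare adjusted with unadjusted analyses directly.

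**Step 1, no early score.** Model: later outcome on A2 and A1, residual df = n − 3. The detectable difference d0 solves the noncentral F power equation with noncentrality d²n/4.

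**Step 2, truncation.** Restricting to slow sites narrows the early score. With a fraction q slow, b = Φ⁻¹(q) and φ the normal density at b, the remaining variance is v = 1 − bφ/q − (φ/q)². The within-slow correlation is r′ = r√v / √(1 − r² + r²v). For q = .2, .5, .8, v = .219, .363, .583. Then r = .5 becomes .26, .33, .40, and r = .7 becomes .42, .51, .60.

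**Step 3, with the early score.** Residual df = n − 4 gives d1. The detectable difference is d1 × √(1 − r′²) × √((n − 4)/(n − 5)), where the last factor is the cost of chance covariate imbalance.

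| Slow sites | d0 | d1 | Imbalance factor | √(1 − r′²), r = .5 / .7 | Adjusted, r = .5 / .7 |
|---|---|---|---|---|---|
| 8 | 2.48 | 2.66 | 1.155 | .965 / .909 | 2.96 / 2.79 |
| 10 | 2.07 | 2.13 | 1.095 | .960 / .896 | 2.24 / 2.09 |
| 14 | 1.64 | 1.66 | 1.054 | .953 / .879 | 1.67 / 1.54 |
| 18 | 1.41 | 1.42 | 1.038 | .944 / .861 | 1.39 / 1.27 |
| 28 | 1.10 | 1.10 | 1.022 | .915 / .801 | 1.03 / 0.90 |

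For 10 and 14 sites, q = n/36.

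**Step 4, break-even.** Adjustment pays only if r′ exceeds √(1 − (d0/(d1 × imbalance factor))²): about .59 with 8 sites, .28 with 18 and .21 with 28. With 8 sites even r = .7, which truncates to .42, falls short. At 10 sites there is no gain at either correlation. At 14 there is a small loss at r = .5 and a gain at r = .7. The drop rule of about 14 comes from this.

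**Check by simulation** (5,000 runs per setting, truncation included). With 18 sites, power goes from .80 to .81 at r = .5 and from .80 to .88 at r = .7. With 28 sites it goes from .79 to .85 and from .80 to .93. With 8 sites it falls from .80 to about .70 at r = .5. Test size was .044 to .052.

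**The case against.** The strongest reply is that the plan does not shut the early score out. It promises an analysis of covariance on pre-post scores, and O1 is undefined. The documents name no site testing score from before the program, which itself creates the sites. For mobilization, the site-level pre score could therefore be this very count. That stands: a reader might infer that the plan ignores or discards the early score, and the documents do not support that. They show only that the score is not named as the Question 2 covariate. The reply does not rescue the shared equation, because reading O1 this way puts a post-A1 variable into Question 1.

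A second reply is that the gain rests on an assumed correlation and is not available across the SAP's whole range. That also stands. A reader might infer that adjustment sharpens the contrast for any number from 8 to 28; the table shows a loss at 8. Nor do the documents describe how widely slow sites differ in early testing, so no claim about that spread can be made.

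A third reply is that the covariate does not make Question 2 well powered. That is right. If the SAP's .54 for 18 sites is read as a standardized difference, power is about .19 unadjusted, and about .19 and .22 adjusted at r = .5 and .7.

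**Conclusion.** The point holds as one of precision and of model definition. O1 is undefined. The early score precedes A2 and is named only as a cutoff. No single covariate can be a baseline for A2 while staying clear of the A1 effect. The randomized Question 2 contrast is unbiased without the score, so nothing here says that its result would be wrong.

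For all-site correlations of .5 to .7, the detectable difference falls by about 1.5% to 10% with 18 slow sites (1.41 to 1.39-1.27 SD) and by about 6% to 18% with 28 (1.10 to 1.03-0.90 SD). With 8 it rises by about 19% to 12% (2.48 to 2.96-2.79 SD). These figures rest on the assumed correlations, 1:1 allocation and normality. They apply to a score on the scale that is cut at 80% of capacity; a Latinx-specific rate would be truncated differently. They concern the site testing outcome only. SAP 4.3.b in one place also attaches individual health behaviors to Question 2, and a site's test count is not a baseline for those.

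**What to change.** In SAP 4.3.d, for the site testing outcome only:

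1. Pre-specify a separate Question 2 model in slow sites: later testing outcome on A2, A1 and the continuous first-two-event score, on the same scale as the outcome.
2. Define O1 in the Question 1 model as a named score from before A1, or state that none is available. Keep the first-two-event score out of that model.
3. State in advance that the early score is dropped when about 14 or fewer sites are slow.
4. State that the score is not used as a baseline for individual health behaviors.

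This needs SAP wording and a variable already collected. It costs one residual degree of freedom and a small loss if the correlation proves low. With 18 sites and no correlation at all, the detectable difference would rise by about 4% (1.42 × 1.038 = 1.47, against 1.41).

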#### 4.3.b Embedded AIS Research Questions and Aims

The specific research questions and aims are the following. Question 1a: Is Basic Outreach plus Promotoras Comunitarias more effective for maximizing testing capacity than Basic Outreach? Question 1b: For individuals tested, is Pamphlet plus Promotoras de Salud more effective than Pamphlet only in supporting positive health behaviors for individuals tested? [(A+B+C+D) vs (E+F+G+H)]. Research Aim Question 2: Among slow responding sites, does the mobilization intervention yield an increase in individual positive health behaviors and in site testing capacity? [(D+H) vs (C+G)].

Each of these AIS research questions is depicted in Figures 4.3.2 through 4.3.3:

**Question 1a:** Is Basic Outreach plus Promotoras Comunitarias more effective for testing capacity than Basic Outreach alone, for Latinx communities?

**Question 1b:** For individuals tested, is Pamphlet plus Promotoras de Salud more effective than Pamphlet only in supporting positive health behaviors for individuals tested, and increasing site testing rates?

**Aim 1a:** Is Basic Outreach plus Promotoras Comunitarias more effective for testing capacity than Basic Outreach alone?

**Aim 1b:** For individuals tested, is Pamphlet plus Promotoras de Salud more effective than Pamphlet only in supporting positive health behaviors for individuals tested, and increasing testing rates?

[figure not shown]

Figure 4.3.2

**Research Aim Question 2:** Among slow responding sites, does the mobilization intervention yield an increase in site testing capacity?

**Aim 2:** Among slow responding sites, does the mobilization intervention yield increase in site testing capacity?

[figure not shown]

Figure 4.3.3

In addition to research questions 1 and 2, the SMART design also allows for an omnibus comparison; after starting with Basic Outreach or Basic Outreach + Promotoras Comunitarias, we can examine which of the embedded adaptive intervention strategies is more effective overall for testing capacity and health behavior maintenance [A vs B vs C vs D vs E vs F vs G vs H]. Although not a specific aim of the proposed study, agencies and stakeholders may be particularly interested in this question and our study design will allow us to test this, focusing on the combined R1 and R2 strategies.

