Finally, when considering power for individual level data, a mixed model with two levels (individuals nested within sites) we must consider full capacity scenarios where implementation is realized at full capacity (roughly 3600 tests) to scenarios that obtain a smaller number of individual tests based on response patterns by site. In this case, that is the balanced scenario shown in Figure 4.3.1 given half of the sites are slow responding. That scenario projects a maximum of 2520 level-1 testing units sampled from 36 sites and achieves .80 power to detect a difference of .22 (a small effect) among the group conditions for randomization 1 conditions A1, randomization 2 conditions A2, and their crossed A1A2 interaction, and an intraclass correlation of .05 for the test of comparative intervention strategies from the primary equation shown above. Thus, the study is adequately powered for all multilevel data scenarios for minimum response to maximum response to detect small effect sizes. Power for individual comparisons among the 4 embedded AISs is shown in Figure 4.3.f.

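### Question 2 concerns slow-responding sites, but the SAP writes no model for that contrast and gives no individual-level power for it

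*SAP*

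**What the plan says.** SAP section 4.3.b states Question 2 three times. The opening paragraph asks: "Among slow responding sites, does the mobilization intervention yield an increase in individual positive health behaviors and in site testing capacity". The later research question and Aim 2 mention site testing capacity only. The contrast is (D+H) vs (C+G).

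Section 4.3.d repeats that contrast and says the question is "which A2 strategy works best for slow-responding sites". It then prints one equation, introduced as the model for finding the best strategy, with terms A1, A2, A1A2 and a pre-test covariate O1. The coding is left to Table 4.3.1, which is not in the text available for review.

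Section 4.3.a defines response by a threshold of 80% of testing capacity. It places the second randomization after the first 4 weeks and does not restrict it to slow sites.

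Section 4.3.f sets the convention: "We chose a power convention of .80 with a two-sided alpha level of .05". With the site as unit, it gives Question 2 detectable effects of .54 for 18 slow sites, 1.3 for 8 and .35 for 28. At the individual level it takes "a maximum of 2520 level-1 testing units sampled from 36 sites" and says this "achieves .80 power to detect a difference of .22 (a small effect) among the group conditions". The terms covered include "randomization 2 conditions A2, and their crossed A1A2 interaction", with "an intraclass correlation of .05 for the test of comparative intervention strategies from the primary equation shown above". It concludes that power for small effects is adequate in every multilevel scenario, from lowest to highest response.

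**The concern.** The letters A to H denote eight cells. A1 by A2 gives only four means at any value of O1, so the printed equation cannot separate the slow-site cells C, D, G and H from the rest. O1 cannot stand in for response status, because it is a pre-test measure and response is judged after first-stage outreach. One analyst could fit the equation to all sites and report A2; another could restrict the analysis to slow sites. Both could say they followed the SAP, and they would be estimating different quantities.

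The power section adds a second problem. If health behaviors belong to Question 2, the relevant data come from the slow sites only, while the single individual-level figure draws on every site. A reader of the concluding claim would think the slow-site comparison of health behaviors well powered, and nothing in the SAP shows that it is.

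**Working it through.** **Inputs.** From SAP 4.3.f: two-sided alpha .05, power .80, ICC .05, 2,520 people in 36 sites (mean 2,520/36 = 70), full capacity about 3,600 (3,600/36 = 100 per site), and 8, 18 or 28 slow sites. Assumed: equal allocation to the two A2 conditions, and 40 to 100 people per slow site. The SAP does not state the per-site count. Forty is one value that fits the balanced scenario (18×100 + 18×40 = 2,520); 100 is full capacity.

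**Formula.** For J sites of m people, in SD units, SE = 2·√[(ICC + (1 − ICC)/m)/J]. The detectable effect is (1.960 + .842)·SE = 2.802·SE.

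**Step 1: the SAP's own .22.** With J = 36 and m = 70, SE = 2·√(.06357/36) = .0840. The detectable effect is .235 (.243 with t, 32 df), and power at .22 is 74.5% (71.9% with t). With sites of 100 and 40 people it is .240. A covariate explaining about 13% of the variance would give .22 (.235·√.87 = .220), but the SAP states none. This small discrepancy is a separate matter. The .22 clearly belongs to an all-site comparison.

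**Step 2: what the all-site A2 effect estimates.** If mobilization shifts slow sites by δ and responding sites by nothing, the site-averaged A2 difference is δ × (share of slow sites):
- 18 of 36 slow: .50δ. A slow-site effect of .22 appears as .11, with about 26% power at 36 sites of 70; a pooled .22 requires .44 at slow sites.
- 8 of 36 slow: 8/36 = .22δ.

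A 5,000-run simulation of the printed equation, with a slow-site effect of .44 and none elsewhere, gave a mean pooled difference of .222 and a mean slow-site difference of .443. A zero effect at responding sites is the extreme case. Any benefit there raises the pooled figure.

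**Step 3: individual-level detectable effect among slow sites.** Example: J = 18, m = 40 gives SE = 2·√(.07375/18) = .128, and 2.802 × .128 = .359. The t column uses J − 2 df.

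| Slow sites | People per site | SE | Detectable (normal) | Detectable (t) | Power at .22 (normal / t) |
|---|---|---|---|---|---|
| 8 | 40 | .192 | .538 | .647 | 20.8% / 16.1% |
| 8 | 100 | .172 | .483 | .581 | 24.7% / 18.9% |
| 18 | 40 | .128 | .359 | .382 | 40.5% / 36.5% |
| 18 | 100 | .115 | .322 | .343 | 48.1% / 43.6% |
| 28 | 40 | .103 | .288 | .299 | 57.3% / 54.1% |
| 28 | 100 | .092 | .258 | .268 | 66.5% / 63.2% |

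**Step 4: sensitivity to covariate adjustment.** Allowing the same 13% reduction multiplies each effect by √.87 = .933. The normal-approximation ranges become .45 to .50 (8 sites), .30 to .33 (18) and .24 to .27 (28).

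**The case against.** A reader might infer that the SAP tests Question 2 with the all-site A2 coefficient. The documents do not say so. Section 4.3.d names the slow-site contrast, and the printed equation has another stated purpose: comparing the embedded strategies. Averaging over responding and slow sites is correct for that purpose, so omitting response status there is not an error in itself.

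A reader might also infer that .22 is offered as the power for Question 2. It is not. The SAP ties it to the terms of its primary equation, and it matches the comparison it is attached to. Nor does the power section ignore slow sites: it gives site-level Question 2 figures for 8, 18 and 28 of them. Whether those effect sizes are right is not examined here.

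Two further limits stand. Table 4.3.1 is not visible and might code response status, so the absence of such a term is established only for the printed equation. And two of the three statements of Question 2 concern testing capacity alone, so the individual-level gap arises only from the statement that adds health behaviors.

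What the objection leaves untouched is that naming a contrast does not specify a model or a subset rule, and that the concluding power claim makes no exception for the slow-site question.

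**Conclusion.** The point holds in two limited parts. First, no fitted model or subset rule is printed for Question 2, and the all-site A2 effect is a different quantity. At worst, with half the sites slow and no effect elsewhere, it is half the slow-site effect. On its own this is close to missing detail.

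Second, the general claim of adequate power for small effects is wrong as written once health behaviors are part of Question 2. At 18 slow sites the detectable effect is about .32 to .38, and at 8 sites about .48 to .65, counting both approximations. The SAP calls .27 small and .35 moderate, although it applies those labels to site-level effects. At 28 sites the range is .26 to .30, where the claim is arguable. With 18 slow sites, power at .22 itself is roughly 37% to 48%.

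These figures rest on the SAP's ICC of .05, equal A2 allocation and the assumed 40 to 100 people per slow site. At 18 or 8 slow sites, no count in that range brings the detectable effect down to .22. They also assume that the second randomization takes place; the protocol's overall study design describes only the first, and the two documents should be reconciled on this.

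**What to change.** In 4.3.d, state that Question 2 is tested by the A2 effect among sites below the 80% threshold after the first 4 weeks. Either restrict the analysis to those sites, or add response status R and A2×R to the model and name the slow-site A2 effect as the test. Keep the all-site A2 term for the overall strategy comparison.

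In 4.3.f, confine the .22 and the general adequacy statement to the all-site comparison. Then choose one of two routes. Either add individual-level detectable effects for Question 2 over 8 to 28 slow sites, with the number of people per slow site stated as an assumption, or remove health behaviors from the opening statement of Question 2 in 4.3.b so that it agrees with the other two.

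The cost is some SAP wording, one extra model and, if health behaviors stay in Question 2, a less favourable stated effect. No change to the design or data collection is needed.
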